Follow-up blood collection, biochemical assays for circulating 25(OH)D, EPA and DHA are those of the parent VITAL trial, described in Partners' IRB approved protocol 2009-P-00127; clinicaltrials.gov number 01169259.

Biochemical assays for Inflammatory biomarkers: IL-6, TNF receptor2 (TNFR2) and hsCRP assays. (Children's Hospital, Boston, MA, [name]) IL-6 will be measured by an ultra-sensitive quantitative sandwich enzyme immunoassay from R&D Systems. IL-6 is quantified in pg/ml and assay sensitivity is 0.94 pg/mL. IL-6 is a strong predictor of cardiovascular disease and type 2 diabetes^{23, 412, 413}, suggesting that a single sample represents long-term levels. $TNF\alpha$ cannot be reliably measured in stored plasma as it degrades rapidly. TNFR2 expression parallels $TNF\alpha$ levels and is a surrogate marker for inflammation^{414, 415}. TNFR2 will be measured by a quantitative sandwich ELISA assay from R & D Systems. Day-to-day assay variabilities at concentrations of 54.8, 252 and 356 pg/mL are 8.8, 3.7 and 5.8%, respectively. TNFR2 stability was assessed in 17 fresh blood samples, at baseline, and after a delay of 24 hours and 36 hours, and the CV was 0.8 for the comparison of 0 to 36 hours (personal communication, [name]). High sensitivity CRP will be measured by high sensitivity latex-enhanced immunonephelometric assay on a BNII analyzer (Dade Behring, Newark, Delaware), with a coefficient of variation of < 5%. CRP levels by this technique, in mg/L, are predictive of cardiovascular disease and type 2 diabetes in cohort studies^{23, 416}.

Knee Pain Assessments Among those who screen positive for chronic knee pain (knee pain with walking 2-3 blocks, pain > 5 days per week for > 1 year, and a doctor's diagnosis of knee OA and no history of total knee replacement) during the run-in phase, baseline knee pain symptoms will be assessed prior to randomization and receipt of any study medications. Thereafter, knee pain symptoms will be assessed annually during the same season (month) in this chronic knee pain subcohort of 2000 participants. We will use the following validated, short

instruments to assess knee pain, analgesic use and depression:

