a. Western Ontario McMaster Universities (WOMAC) Knee Osteoarthritis Index Developed in 1988, the WOMAC knee questionnaire is a multidimensional measure of pain, stiffness, and physical functional disability consisting of 24 items graded in a numerical rating scale ranging from 0 (“no symptoms”) to 10 (“extreme symptoms”)^{417, 418}. It is the most widely used and accepted measure for monitoring⁴¹⁹ the course of the disease or to determine the effectiveness of anti-rheumatic medications in many knee OA trials. As several studies pointed to redundancy in the WOMAC function scale^{68, 420}, Whitehouse and colleagues have developed and tested a reduced WOMAC function scale that contains seven functional items⁴²¹. This scale, when tested in 1578 total joint replacement patients, had a Cronbach’s alpha of 0.85 with the WOMAC, indicating reliability and responsiveness to change was even greater than that of the extended scale. We will utilize the reduced WOMAC function scale, along with the pain, stiffness, and overall WOMAC scales.

b. Analgesic medications Participants will be asked to report which medications they are taking from a short list of typical medications taken for knee pain, how frequently and for how long they have taken them. Medication use will be categorized as follows: (0) none, (1) acetaminophen/non-steroidal anti-inflammatory drugs (NSAIDs), (2) narcotics/adjunctive pain medications (such as anti-depressants and antiepileptics). A decrease in analgesic medication use (from higher to lower category) will be considered as a secondary outcome, and analgesic use will also be included as a covariate in other knee pain analyses.

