c. Mental Health Inventory-5 (MHI-5) from the Short- form (SF-36) Health Survey The SF-36 is a widely-used and well-validated questionnaire that assesses eight domains of general health⁴²²⁻⁴²⁵. The SF-36 includes a subscale of five questions about mental health (the Mental Health Index-5, MHI-5)⁴²⁶. The MHI-5 is comprised of 5 questions and there are six possible responses to each question, scored between 1 and 6. Individuals’ scores thus range from 5 to 30. This is then transformed into a variable from 0-100 using a standard linear transformation. This subscale will provide useful a covariate as mental health could potentially explain some of the outcome variance. The responses range from “never” to “most of the time” and will be scored following a standard protocol. The recommended cut-off for a mood disorder/depression is a score of 65 on the mental health questions (MHI-5). The SF-36v2, its most recent version, is copyrighted, and we have obtained permission to use it from the Medical Outcomes Trust and QualityMetric Incorporated.

Procedures for the Validation of Deaths, Compliance and Data Management will be those of the parent VITAL trial, described in Partners’ IRB approved protocol 2009-P-00127; clinicaltrials.gov number 01169259.

For studies involving treatment or diagnosis, provide information about standard of care at Partners (e.g., BWH, MGH) and indicate how the study procedures differ from standard care. Provide information on available alternative treatments, procedures, or methods of diagnosis.

This trial will not affect standard of care for any disease state. The medications tested will not be for treatment or diagnosis.

Describe how risks to subjects are minimized, for example, by using procedures which are consistent with sound research design and which do not unnecessarily expose subjects to risk or by using procedures already being performed on the subject for diagnostic or treatment purposes.

Procedures to minimize risks including recruitment and informed consent, protection of medical records and personal health information, minimization of risks of the trial medications, DSMB structure and oversight, will be those of the parent VITAL trial, described in Partners’ IRB

approved protocol 2009-P-00127; clinicaltrials.gov number 01169259.

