When specimens or data collected by research collaborators outside Partners will be sent to Partners investigators, indicate from where the specimens/data will be obtained and whether the specimens/data will contain identifiers that could be used by Partners investigators to link the specimens/data to individual subjects. When appropriate, submit documentation of IRB approval and a copy of the IRB-approved consent form from the institution where the specimens/data were collected.

Not applicable.

Protocol Biostatistical Analyses

Separate analyses will be conducted for the 3 endpoints and for the 2 nutritional supplements, vitamin D and omega-3 fatty acids. Analyses of treatment effects will be based on the intent-to-treat principle. The first analysis will compare baseline characteristics by randomized treatment

assignment to ensure that balance was achieved by the randomization. Characteristics to be examined include known risk factors for autoimmune diseases, systemic inflammation, and chronic knee pain including: age; gender; race/ethnicity; family history of autoimmune disease; BMI; smoking; alcohol use; physical activity; co-morbid medical conditions such as hypertension, hyperlipidemia, diabetes, and cardiovascular disease; and baseline vitamin D and omega-3 fatty acid levels as assessed by dietary questionnaire in all participants and blood assays in the case-cohort subsample. The large sample size, as well as successful balance of known potential confounders, will provide assurance that unmeasured or unknown potential confounders will also be equally distributed across randomized treatment groups. For autoimmune disease, we will estimate the intervention effects on the primary endpoint of total incident autoimmune disease. For inflammatory biomarkers, we will assess changes in linear biomarkers (log transformed if necessary). For chronic knee pain, the primary endpoint will be assessed by the WOMAC pain scale; secondary analyses will test for decreases in WOMAC stiffness, function and global scales, as well as analgesic use separately. Data analyses will be performed using SAS 9.2 (SAS Institute Inc., Cary, North Carolina).

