Autoimmune Disease Incidence. In this 2x2 factorial design, the primary aim is to compare the main effects of intention-to-treat with vitamin D and with fish oil upon autoimmune disease incidence. Initially, we will compare Kaplan-Meier curves to graphically display the survival functions across different treatment groups and a log-rank test to test the difference. We will use Cox proportional hazards models to assess the main and interaction effects of the treatment groups. The unadjusted risk ratios and their 95% CIs will be used to measure the strength of risk across different treatment groups. The proportional hazard assumption will be tested based on the smoothed plots of the scaled Schoenfeld residuals³⁸⁶. To estimate the cumulative incidence function, a nonparametric estimate will be obtained using the Kaplan–Meier method. Given randomization and blinding of 20,000 individuals in this RCT, most important covariates will be equally distributed. But, in secondary analyses, we will assess the effects of controlling for age, sex and other possible strong predictors, such as family history of autoimmune disease; baseline levels of inflammatory biomarkers, vitamin D, EPA and DHA; dietary vitamin D, EPA and DHA intake; BMI and physical activity.

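### Could adjusting the WOMAC models for analgesic use, itself a secondary outcome, distort the intent-to-treat effect on knee pain?

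*Combined protocol and SAP*

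**What the plan says.** Under Knee Pain Assessments, the subcohort completes a baseline assessment before randomisation. "Thereafter, knee pain symptoms will be assessed annually during the same season (month) in this chronic knee pain subcohort of 2000 participants". The tools are described as "instruments to assess knee pain, analgesic use and depression", so analgesic use will very probably be recorded at every annual contact.

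Item b (Analgesic medications) gives the variable two roles in one sentence. As an outcome: "A decrease in analgesic medication use (from higher to lower category) will be considered as a secondary outcome". As a covariate: "analgesic use will also be included as a covariate in other knee pain analyses". The covariate role has no time point. Item c gives the MHI-5 a similar undated role: "This subscale will provide useful a covariate as mental health could potentially explain some of the outcome variance".

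Protocol Biostatistical Analyses opens with a general commitment: "Analyses of treatment effects will be based on the intent-to-treat principle". Its Chronic Knee Pain paragraph makes the annual WOMAC pain subscale the primary outcome. It uses two-way ANOVA or Kruskal-Wallis without covariates and a linear mixed model for the adjusted repeated-measures analysis. Medication use and depression are listed among the correlates of knee pain. Balance is to be checked at baseline, and the listed factors are then adjusted for as potential confounders.

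Item b defines the top analgesic category as "2) narcotics/adjunctive pain medications (such as anti-depressants and antiepileptics"; the Chronic Knee Pain paragraph shortens it to narcotics.

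**The concern.** A variable that treatment may alter is not a neutral covariate. The plan itself allows that the supplements may reduce analgesic use, since it tests for that. If a participant's use at each follow-up visit entered the WOMAC mixed model, the treatment coefficient would describe the difference in pain at a given level of analgesic use. That is a different quantity from the intent-to-treat effect, and it would be misread against the minimal clinically important difference (MCID) of 0.75 for WOMAC pain.

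The wording leaves room for this. Follow-up values will exist, a mixed model accepts time-varying covariates, and item b does not say baseline. Elsewhere the plan does label covariates: the autoimmune paragraph adjusts for "baseline levels of inflammatory biomarkers, vitamin D, EPA and DHA". A reader could take the missing label in item b as deliberate. At stake would be the adjusted estimate for the primary knee outcome.

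**Working it through.** **1. The plan's own figure.** Inputs from Power calculations, c. Chronic knee pain: SD 2.25, MCID 0.75, type I error 0.05 (taken as two-sided), 2000 participants, 80% for loss and compliance. With four groups, 2000/4 × 0.80 = 400 per group.

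- Standard error = 2.25 × √(2/400) = 0.159
- Power = Φ(0.75/0.159 − 1.96) = Φ(2.75) = 0.997, against 0.99 in the plan's table

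The stated power reproduces to within a point. It does not depend on the analgesic covariate.

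**2. What follow-up adjustment would do.** Let *a* be the effect of treatment on follow-up analgesic category and *b* the WOMAC slope per category within arm. In a linear model the adjusted coefficient = total effect − *a* × *b*. The documents give neither *a* nor *b*, so the values below are assumptions. Power keeps SD 2.25 and 400 per group.

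| *a* | *b* | Adjusted coefficient | Power |
|---|---|---|---|
| 0 | any | −0.75 | 0.997 |
| −0.1 | +1.0 | −0.75 + 0.10 = −0.65 | 0.983 |
| −0.2 | +1.0 | −0.75 + 0.20 = −0.55 | 0.933 |
| −0.3 | +1.5 | −0.75 + 0.45 = −0.30 | 0.470 |
| −0.2 | −0.5 | −0.75 − 0.10 = −0.85 | >0.999 |

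The shift can go either way, and it vanishes if treatment leaves analgesic use unchanged.

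**3. What baseline adjustment does.** This was simulated with 400,000 records per scenario, one follow-up visit, underlying pain SD 2.25 and a treatment effect of 0.75 on underlying pain. Analgesic category depends on pain with an assumed strength. Assumed relief is 0 or 0.5 points per category.

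| Link from pain to use | Relief | Unadjusted | Baseline-adjusted | Follow-up-adjusted |
|---|---|---|---|---|
| none | 0.5 | −0.754 | −0.756 | −0.754 |
| weak | 0.5 | −0.715 | −0.715 | −0.663 |
| moderate | 0.5 | −0.676 | −0.676 | −0.499 |
| strong | 0.5 | −0.651 | −0.649 | −0.353 |
| strong | 0 | −0.740 | −0.741 | −0.361 |

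Across all scenarios with a treatment effect, including 1 point of relief per category, unadjusted and baseline-adjusted estimates differed by at most 0.003. With no treatment effect, the unadjusted, baseline-adjusted and follow-up-adjusted estimates were 0.002, −0.003 and 0.003, so even follow-up adjustment produced no false benefit there.

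**4. Which reading the plan supports.** Everything therefore turns on the text.

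- *Chronic Knee Pain* treats the listed factors as potential confounders, straight after promising a check of balance at baseline. A value measured after randomisation cannot confound a randomised comparison.
- *Inflammatory Biomarkers* uses the same construction, also with medication use in the list. It checks baseline balance and then adjusts for the same items, most naturally the baseline characteristics just named. The knee paragraph repeats this pattern explicitly.
- *Statistical issues in resampling from a RCT* ties multivariable control to imbalance in sample characteristics, which is a baseline notion.
- The opening paragraph compares known risk factors for chronic knee pain as baseline characteristics, and *Secondary Analyses* speaks of baseline risk factors for it.
- No section mentions concurrent, follow-up or time-varying analgesic use as a covariate.

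**5. The category label and model.** The shorter label in Chronic Knee Pain can be read as shorthand for the fuller list in item b. Pairing a three-level scale with a binary mixed model is also reconcilable: item b's outcome is a drop in category, which is yes or no at each visit.

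**The case for a change.** The best case for a change is that item b is unconditional and undated, and that leaning towards baseline is not the same as saying so. Two analysts could each claim to follow the plan and report different adjusted WOMAC estimates. The MHI-5 is justified by explained variance rather than confounding, so the confounder argument does not plainly cover item c. The label is used elsewhere, and adding it here would cost one sentence and no new data.

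Part of this stands. The literal gap is real, and so is the difference in category 2. That difference reaches the covariate as well as the secondary outcome, because item b uses one variable for both.

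The rest is weaker. Explaining outcome variance is the ordinary reason for including a baseline covariate, and Chronic Knee Pain lists the MHI-5 with the other factors checked at baseline. The contrast in labelling proves little: in the autoimmune paragraph, dietary intake, BMI and physical activity carry no baseline label of their own, and nobody would take them as time-varying. Harm also needs two conditions together: the less natural reading and an effect of treatment on analgesic use. The unadjusted comparison is unaffected either way.

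**Conclusion.** The concern does not call for a change. Item b leaves out a time point, but the analysis section governs how covariates are used. Its natural reading is adjustment for analgesic use and MHI-5 measured before randomisation. Followed that way, the mixed model estimates the intent-to-treat effect, with differences of 0.003 points or less in the simulations against an MCID of 0.75.

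The size of any distortion under the other reading is unknown. The adjusted effects of 0.30 to 0.85, and power as low as 0.470, come entirely from assumed links between treatment, pain and analgesic use. They show that the timing would matter, not that the plan has chosen wrongly. The conclusion rests on reading item b together with Chronic Knee Pain; it would change if the plan anywhere called for follow-up analgesic use in the WOMAC model, and it does not.

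The category 2 difference is a clerical slip. It could affect how participants taking only adjunctive drugs are coded, and the fuller list in item b gives the analyst a workable definition.

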Inflammatory Biomarkers. In a randomly selected subcohort of 2000 participants, blood will be collected at both baseline and follow-up and changes in levels of plasma biomarkers of inflammation will be investigated. As inflammatory biomarkers are associated with age, BMI, medication use and cigarette smoking, we will again ensure that baseline characteristics are balanced in the four treatment groups in this subcohort and will additionally adjust for them in our analyses. Inflammatory Biomarkers (hsCRP, IL-6, TNFR2) will be analyzed as continuous outcomes. Descriptive statistics such as the minimum, maximum, range, median, and mean are used to summarize the variable as well as detect outliers and missing values. Exploratory graphical techniques such as Boxplots, Histograms, Quantile-Quantile plots, and Stem and Leaf plots will be used to further examine the distribution of each biomarker. Natural log transformation may be necessary based on our past analyses¹⁰⁵. Unadjusted treatment effects will be evaluated using two-way Analysis of Variance (ANOVA) or Kruskal–Wallis nonparametric test. Multiple linear regression will be used to test the association between the biomarkers (or transformed scale) and treatment groups, while adjusting for age and gender. Model assumptions and goodness of fit will be evaluated using applicable techniques³⁸⁷. In a secondary analysis, additional adjustment for the other potential predictors including baseline biomarkers will be performed.

Chronic Knee Pain. In a separate subcohort of approximately 2000 individuals with baseline chronic daily knee pain and no history of total knee replacement surgery, we will evaluate changes in level of knee pain over the course of the RCT. The annual measure of WOMAC knee pain subscale will be the primary outcome. Angst and colleagues examined data from 122 prospectively-followed individuals with knee OA in a comprehensive rehabilitation program to define the minimally clinically important difference (MCID) in WOMAC scores (range 0-10), for

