pain, stiffness and function³⁸⁸. Analgesic use will be secondary outcome, defined on a scale of 0-2: 0 (none), 1 (NSAIDs or acetaminophen only) and 2 (narcotics). As chronic knee pain is associated with age, BMI, medication use, comorbidities and depression (MHI-5), we will again ensure that baseline characteristics are balanced in the four treatment groups in this knee pain subcohort and will additionally adjust for these potential confounders in our analyses. Similarly, we will analyze repeated measures of WOMAC knee pain score, stiffness score, function score and globe score as continuous outcomes. The descriptive statistics and the distribution of each outcome variable will firstly be examined. Transformation will be considered if applicable. We will use two-way analysis of variance (ANOVA) or Kruskal–Wallis test for bivariable analysis and general linear mixed model for multivariable repeated measure analysis. For another secondary outcome, we will assess the effects of the supplements upon analgesic use, classified as: no medications, acetaminophen or non-steroidal use; and narcotic medication). Generalized linear mixed models for repeated binary outcomes will be used to examine the adjusted associations.

Statistical issues in resampling from a RCT. Our investigations of the effects of these agents on biomarkers of systemic inflammation and knee pain will not utilize the entire 20,000 individuals enrolled in the funded VITAL trial. Rather, each will follow a selected subcohort of approximately 2000 individuals. It is possible that these individuals will not be drawn completely equally or randomly from the 4 treatment groups. Possible unbalance of sample characteristics will be evaluated and be controlled for in multivariable analyses.

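### Kruskal-Wallis, named as the alternative to two-way ANOVA, is a one-way test; run on the four treatment groups it cannot attribute an effect to vitamin D or to fish oil

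*Combined protocol and SAP*

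**What the plan says.** All references are to the Protocol Biostatistical Analyses section of the combined document.

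- **Opening paragraph:** "Separate analyses will be conducted for the 3 endpoints and for the 2 nutritional supplements, vitamin D and omega-3 fatty acids".
- **Inflammatory Biomarkers:** "Unadjusted treatment effects will be evaluated using two-way Analysis of Variance (ANOVA) or" a Kruskal-Wallis test. Linear regression adjusted for age and gender follows. The paragraph allows for a log transformation, and gives no rule for when Kruskal-Wallis would be used instead of ANOVA.
- **Chronic Knee Pain:** "We will use two-way analysis of variance (ANOVA) or" Kruskal-Wallis for the bivariable step, followed by a general linear mixed model for the repeated measures.
- **Autoimmune Disease Incidence:** "the primary aim is to compare the main effects of intention-to-treat with vitamin D and with fish oil upon autoimmune disease incidence". The first step is Kaplan-Meier curves to "graphically display the survival functions across different treatment groups and a log-rank test to test the difference". Then: "We will use Cox proportional hazards models to assess the main and interaction effects of the treatment groups".

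Nowhere does the plan state how many groups enter the Kruskal-Wallis or log-rank test, and it gives no stratified or factorial version of either.

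**The concern.** The factorial question is what each agent does. Two-way ANOVA answers it with one test per factor. Kruskal-Wallis has no second factor. Put in place of two-way ANOVA, it would most naturally be given the four treatment groups, which both the biomarker and the knee pain paragraphs mention shortly beforehand when they discuss baseline balance. It then tests whether any of the four groups differs, and a significant result could come from either agent or from both.

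Two things are at stake. The unadjusted rank analysis might not answer the question asked. And where one agent works and the effect is modest, a non-significant four-group result could stand beside a significant main-effect result, with nothing in the plan to say which governs.

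**Working it through.** **1. The plan's own figures.** Under Power calculations, item a, the plan states 81% log-rank power at an observed RR of 0.70, with 150 events in the placebo group. One active cell against the double-placebo cell gives 150 + 0.70 × 150 = 255 events. With the Schoenfeld formula at two-sided 0.05 (sidedness is not stated for Aim 1; this choice reproduces the figure), z = √(255/4) × |ln 0.70| − 1.96 = 7.984 × 0.3567 − 1.96 = 0.89, so power is 0.813. The stated figure reproduces, and it is for a two-group, 1-df test.

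Under item b, the plan states 89% power for a 25% hsCRP reduction, with 500 per group and a two-sided t test on the log scale. The log-scale SD is not given, so it is back-solved: SD = |ln 0.75| × √(500/2) / (1.960 + 1.227) = 0.2877 × 15.81 / 3.187 = 1.43. This is an assumption. Counting compliance as 400 per group gives 1.28 and the same power results.

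**2. Rank tests for hsCRP, one agent effective, four cells of 500.** With δ = −ln(1 − reduction), both tests have noncentrality λ = (3/π) × 500 × (δ/SD)², where 3/π is the efficiency of rank tests for normal data (here, log values). The 1-df and 3-df tests share λ because the ineffective agent adds nothing; only the critical value differs (3.84 v 7.81).

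| Reduction | δ | λ | Four groups, 3 df | One agent, 1 df |
|---|---|---|---|---|
| 25% | 0.288 | 19.4 | 0.97 | 0.99 |
| 20% | 0.223 | 11.7 | 0.83 | 0.93 |
| 15% | 0.163 | 6.2 | 0.53 | 0.70 |

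Simulation agrees: four-group Kruskal-Wallis gave 0.97, 0.83 and 0.52 to 0.54, and the 1-df rank test (van Elteren, or two groups on the margin) gave 0.99, 0.92 to 0.93 and 0.70. The 1-df test was significant while Kruskal-Wallis was not in about one trial in ten at 20% and just under one in five at 15%. At 80% power the 3-df test needs λ = 10.90 against 7.85, or 39% more information.

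**3. Attribution.** If one agent lowers hsCRP by 25% and the other does nothing, four-group Kruskal-Wallis rejects in 97% of trials. A two-group rank test of the inactive agent rejects in 5%, as it should.

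**4. The log-rank test, if it were run on four groups.** With one agent effective, events = 300 + 300 × RR and λ = (events/4) × (ln RR)².

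| RR | Events | λ | Four groups, 3 df | One agent, 1 df |
|---|---|---|---|---|
| 0.70 | 510 | 16.2 | 0.94 | 0.98 |
| 0.75 | 525 | 10.9 | 0.80 | 0.91 |
| 0.80 | 540 | 6.7 | 0.57 | 0.74 |

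**5. Both agents effective.** Take RR 0.80 for each, acting multiplicatively. Cell events are 150, 120, 120 and 96, a total of 486 and a mean of 121.5. For four groups, λ = (28.5² + 1.5² + 1.5² + 25.5²)/121.5 = 12.1, so power is 0.84. For one agent's main effect, λ = (270 − 216)²/486 = 6.0, so power is 0.69. Here the four-group test is more likely to find some difference, though it still does not identify its source.

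**The case against.** The best defence is that the four-group test is an inference. The plan calls for separate analyses of the two supplements, makes main effects the aim, and describes the knee pain test as bivariable. On that reading Kruskal-Wallis would be run on two groups at a time, where it is the Wilcoxon test and raises no difficulty. This stands as far as it goes: the text permits it. But the text does not say it, and a test named as the alternative to a two-factor method is more naturally given all four groups.

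Four stronger readings are tempting and are not supported:

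- *That the plan has no test of main effects.* Two-way ANOVA is named first and tests each agent. The Cox model covers main and interaction effects for Aim 1. The regression and mixed models could do the same for the other aims, although their treatment coding is not stated.
- *That the log-rank test is a four-group test.* The wording is open, the log-rank is only the initial step before Cox, and the stated power reproduces as a two-group test. This is an ambiguity and no more.
- *That the planned power is undercut.* At RR 0.70 even a four-group log-rank would have 0.94, above the stated 81%. At a 25% hsCRP reduction the loss is about 2 points.
- *That Kruskal-Wallis is the planned response to skewed biomarkers.* The plan's stated response is log transformation, and no trigger for the rank test is given.

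It is also fair to say that the power loss depends on only one agent working; step 5 of the working shows the reverse when both do.

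**Conclusion.** The point holds in a limited form and is minor. Kruskal-Wallis is not a like-for-like alternative to two-way ANOVA in a 2x2 factorial. On the natural four-group reading it cannot attribute a result to either agent, whatever its power.

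With one effective agent, the power cost for hsCRP is about 2 points at a 25% reduction, 10 at 20% and 17 at 15%. The last of these lies below the 20% to 40% range in the plan's biomarker power table. These sizes rest on the back-solved log SD of 1.43, log-normal data, equal cells of 500 and no interaction. The log-rank figures also assume proportional hazards. The log-rank wording needs clarifying and is not itself a fault.

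**What to change.** In the Inflammatory Biomarkers and Chronic Knee Pain paragraphs, replace Kruskal-Wallis with a two-group rank test of each agent, stratified by assignment to the other agent (van Elteren). An equivalent 1-df rank test, such as a two-group Wilcoxon test on each margin, would also serve.

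As a clarification only, state in the Autoimmune Disease Incidence paragraph that the log-rank test is a two-group test of each agent stratified by the other.

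The cost is two or three sentences, with no new data, since the strata are the groups already randomised. What is given up is the four-group test's sensitivity to any difference when both agents work. The plan already examines effect modification by the other randomised intervention under Secondary Analyses, and a four-group comparison can be kept there as descriptive if wanted.
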